## 14. Statistical Analysis

Major analysis methods are described below. Details will be specified in a statistical analysis plan prepared separately before the informed consent procedure of the first subject.

For the double-blind period, data from the start of the screening period to the end of the double-blind period will be analyzed. Over the entire study period, data from the start of the screening period to the end of the follow-up period will be analyzed.

Handling of subjects and data in the double-blind period and over the entire study period will be determined before the respective database lock points in the double-blind period and over the entire study period.

All statistical tests will be performed using a two-sided significance level of 5%; however, a two-sided significance level of 15% will be used for the analysis of between-group demographic imbalance. Summary statistics to be presented include the number of subjects, mean, standard deviation, minimum, median, maximum, and quartile.

Data will be tabulated by group and by time point, unless otherwise specified. Baseline is defined as the start date of treatment.

### 14.1 Analysis Sets

Analysis sets are defined as follows: When the full analysis set (FAS) and the per protocol set (PPS) are used as analysis sets, analyses will be performed based on the treatment to which each subject has been assigned. When the safety set (SS) is used as an analysis set, analyses will be performed based on the treatment provided to each subject actually.

- 1) FAS  
Population of subjects given at least one dose of the study drug, meeting the inclusion criterion related to NRS score, and having a baseline mean NRS score.
- 2) PPS (only in the double-blind period)  
Population of subjects excluding the following subjects from the FAS:
  - Subjects not meeting the inclusion criteria
  - Subjects meeting any of the exclusion criteria related to efficacy evaluation
  - Subjects withdrawing from the study before Week 4 in the double-blind period
  - Subjects given < 9 or > 15 doses of the study drug before Week 4 in the double-blind period
  - Subjects changing the dosage and administration of a conditionally permitted concomitant medication or newly using a conditionally permitted concomitant medication before Week 4 in the double-blind period
  - Subjects using a prohibited concomitant drug or therapy before Week 4 in the double-blind period
  - Subjects changing the frequency of dialysis per week or the hemodialysis method before Week 4 in the double-blind period

## 3) SS

Population of subjects given at least one dose of the study drug

## 14.2 Analysis Groups

### 14.2.1 Double-blind period

The analysis sets and subjects included in the analysis sets for the analysis groups are shown in [Table 14.2.1-1](#).

**Table 14.2.1-1 Analysis sets and subjects included in the analysis sets for the analysis groups**

Analysis Groups	Analysis Sets	Subjects included in the analysis set
MR13A9 0.5 µg/kg group	FAS, PPS	Subjects randomized to MR13A9 0.5 µg/kg
	SS	Subjects given MR13A9 0.5 µg/kg
Placebo group	FAS, PPS	Subjects randomized to placebo
	SS	Subjects given placebo

### 14.2.2 Entire study period

The analysis sets and subjects included in the analysis sets for the analysis groups are shown in [Table 14.2.2-1](#).

**Table 14.2.2-1 Analysis sets and subjects included in the analysis sets for the analysis groups**

Analysis Groups	Analysis Sets	Subjects included in the analysis set
MR-MR group	FAS	Subjects randomized to MR13A9 0.5 µg/kg in the double-blind period and entering into the extension period
	SS	Subjects given MR13A9 0.5 µg/kg in the double-blind period and entering into the extension period
P-MR group	FAS	Subjects randomized to placebo in the double-blind period and entering into the extension period
	SS	Subjects given placebo in the double-blind period and entering into the extension period

## 14.3 Disposition of Subjects

For each analysis set and the presence/absence of discontinuation, numbers and percentages of subjects will be presented. For the double-blind period, differences between the groups will be examined.

## 14.4 Demographic and Other Baseline Characteristics

For major subject demographics, summary statistics or numbers and percentages of subjects will be presented overall and by group according to the characteristics of individual data. For the double-blind period, imbalance between the groups will be examined.

## 14.5 Efficacy

The FAS will be used as the primary analysis set for the double-blind period. As a supplementary analysis, the PPS will be used for the primary analysis of the primary variable to determine the robustness of the analysis results.

The FAS will be used as the analysis set for the entire study period.

### 14.5.1 Primary endpoint

The primary endpoint is the NRS score. The assessment time points and their time windows in the screening period, the double-blind period, and the extension period are shown in [Table 14.5.1-1](#). The assessment time point and its time window in the follow-up period are shown in [Table 14.5.1-2](#).

**Table 14.5.1-1 Assessment time points and their time windows in the screening period, the double-blind period, and the extension period**

Period	Assessment time point	Assessment time window a)
Screening period	At Week -1	From Day -13 to Day -7
Double-blind period	At baseline	From Day -6 to Day 1
	At Weeks 1 to 6	From Day $7 \times x - 5$ to Day $7 \times x + 1$ b)
Extension period	At Weeks 7 to 58	From Day $7 \times x - 5$ to Day $7 \times x + 1$ b)

a) The start date of the double-blind period will be regarded as Day 1 and the previous day of the start date of the double-blind period will be regarded as Day -1.

b) x: Number of weeks

**Table 14.5.1-2 Assessment time point and its time window in the follow-up period**

Period	Assessment time point	Assessment time window a)
Follow-up period	At Week 1 of the follow-up period	From Day 1 to Day 7

a) The start date of the follow-up period (the completion date of the extension period or the next day of the date of discontinuation) will be regarded as Day 1.

The mean NRS score at each time point will be calculated as follows. However, if the number of observation days during the assessment period is less than 4 days at the time of calculation of the score at each time point, the data will be deemed as missing:

Mean NRS score at each time point = Sum of the NRS score observed during the assessment time window ÷ Number of days when NRS score was observed during the assessment time window

The change from baseline in the mean NRS score at each time point will be calculated as follows:

Change from baseline in the mean NRS score at each time point = Mean NRS score at each time point – Mean NRS score at baseline

### 14.5.2 Primary variable

The primary variable will be the change from baseline in the mean NRS score at Week 4 of the double-blind period.

### 14.5.3 Analysis of the primary variable

Data obtained up to Week 4 of the double-blind period will be analyzed.

#### 14.5.3.1 Primary analysis

The superiority of the MR13A9 0.5 µg/kg group to the placebo group will be confirmed by performing the analysis using a mixed-effects model for repeated measures (MMRM) with change from baseline in the mean NRS score at each time point as an objective variable; treatment group, time point, and treatment group-by-time point interaction as fixed effects; baseline mean NRS score and the presence or absence of prior treatment with nalfurafine hydrochloride as a dynamic allocation factor as covariates; and subject as a random effect.

The analysis will include all available data obtained at each time point from Week 1 to Week 4 of the double-blind period as objective variables. Estimation will be performed using a restricted maximum likelihood method. An unstructured covariance structure will be used to estimate error variance. If the unstructured covariance structure fails to provide convergence, the structure that minimizes Akaike Information Criterion (AIC), among the Toeplitz, first-order autoregressive, and compound symmetry structures, will be used. The degree of freedom will be adjusted with the Kenward-Roger method.

The adjusted mean change at each time point for each group and its two-sided 95% confidence interval will be presented. The adjusted mean difference in the change at each time point between the placebo group and the MR13A9 0.5 µg/kg group and its two-sided 95% confidence interval as well as the p value will be presented.

#### **14.5.3.2 Sensitivity analysis**

Sensitivity analyses will be performed to determine the robustness of the analysis results. Details of the multiple imputation (MI) method are described separately in the statistical analysis plan.

In the individual analyses, treatment effects will be estimated as in the primary analysis.

##### **1) MI – MMRM**

Multiple imputed data will be generated in the procedures shown below. Each imputation data will be analyzed using the same MMRM model as that for the primary analysis, and the results of the analyses will be combined. Imputation will be performed for all available data obtained at each time point between the baseline and Week 4 of the double-blind period.

- (1) Non-monotone missing data will be imputed with a Markov Chain Monte Carlo (MCMC) method.
- (2) Monotone missing data will be imputed with an imputation formula generated using a regression model developed based on the data from all the groups.

##### **2) Placebo MI – MMRM**

Multiple imputed data will be generated in the procedures shown below. Each imputation data will be analyzed using the same MMRM model as that for the primary analysis, and the results of the analyses will be combined. Imputation will be performed for all available data obtained at each time point between the baseline and Week 4 of the double-blind period.

- (1) Non-monotone missing data will be imputed with an MCMC method.
- (2) Monotone missing data will be imputed with an imputation formula generated using a regression model developed based on the data from the placebo group.

#### **14.5.3.3 Other assessment variables**

##### **1) Change from baseline in the mean NRS score**

Summary statistics will be presented. A one-sample t-test will be used for comparisons within each group. For the double-blind period, a two-sample t-test will be used for comparisons between the placebo group and the MR13A9 0.5 µg/kg group.

##### **2) Mean NRS score**

Summary statistics will be presented.

---

3) Percentage of subjects with improvement in the mean NRS score

The number and percentage of subjects with improvement in the mean NRS score will be presented. For the double-blind period, a Fisher's exact test will be used for comparisons between the placebo group and the MR13A9 0.5 µg/kg group. Subjects with improvement are defined as shown below.

- Subjects with 3-point improvement: Change from baseline in the mean NRS score is  $\leq -3$
- Subjects with 4-point improvement: Change from baseline in the mean NRS score is  $\leq -4$

#### **14.5.4 Secondary endpoints**

1) Itch score based on the Shiratori's severity criteria

The mean itch score and change from baseline at each time point will be calculated using the same calculation formula as that for the mean NRS score and change from baseline shown in “[14.5.1 Primary endpoint](#).”

For changes from baseline, the same analysis as “[14.5.3.1 Primary analysis](#)” will be performed on the data obtained up to Week 4 of the double-blind period. However, the covariate of the model will be the baseline of the data to be analyzed. The same analysis as “[14.5.3.3 1\) Change from baseline in the mean NRS score](#)” will be performed.

For measurements, the same analysis as “[14.5.3.3 2\) Mean NRS score](#)” will be performed.

2) Overall Skindex-16 score and total 5-D itch scale score

For changes from baseline, analysis of covariance with treatment group as a fixed effect and baseline score as a covariate will be performed on the data obtained at the end of the double-blind period. The same analysis as “[14.5.3.3 1\) Change from baseline in the mean NRS score](#)” will be performed.

For measurements, the same analysis as “[14.5.3.3 2\) Mean NRS score](#)” will be performed.

3) PGIC(Patient Global Impression of Change)

The number and percentage of subjects with global symptoms will be presented. For the double-blind period, a two-sample Wilcoxon test will be used for comparisons between the placebo group and the MR13A9 0.5 µg/kg group.

### **14.6 Safety**

The SS will be used as the analysis set.

#### **14.6.1 Adverse events and adverse drug reactions**

For the double-blind period, analysis will include events occurring between the start of study treatment in the double-blind period and the end of the double-blind period. For the entire study period, analysis will include events occurring between the start of study treatment in the double-blind period and the end of the follow-up period.

Adverse events of special interest will also be summarized in the same manner.

1) Incidence of adverse events and adverse drug reactions

The number of events, the number of subjects experiencing events, the incidence of events and its two-sided 95% confidence interval will be presented. For the double-blind period, a Fisher's exact test will be used for comparisons between the placebo group and the MR13A9 0.5 µg/kg group, and the between-group difference in incidence and its 95% confidence interval will be presented.

2) Incidences of adverse events and adverse drug reactions (serious events and events leading to discontinuation)

The numbers of events, the numbers of subjects experiencing events, and the incidences of events will be presented for all events, events leading to death, serious events other than death, and events leading to discontinuation.

3) Occurrence of adverse events and adverse drug reactions

The number of subjects experiencing events and the incidence of events will be presented for all events and by primary SOC and PT.

4) Occurrence of adverse events and adverse drug reactions (by severity)

The numbers of events by severity will be presented for all events and by primary SOC and PT.

5) Occurrence of adverse events and adverse drug reactions (by time of onset)

For the entire study period, the number of subjects experiencing events and the incidence of events for all events and by primary SOC and PT will be presented by time of onset.

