#### Sample Size:

- Double-blind period: The study will enroll 86 subjects each MR13A9 0.5 µg/kg group and the placebo group (172 in total).
- Extension period: The study will enroll 100 subjects who complete 58-week treatment.

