#### **8.5.3.5 Randomization of subjects**

Based on the treatment assignment table prepared by the person responsible for treatment assignment, the subject registration center will randomly assign subjects eligible for tertiary registration to either the MR13A9 0.5 µg/kg or placebo group at a ratio of 1:1 by a dynamic allocation method using two stratification factors: Prior treatment with nalfurafine hydrochloride notified by the medical institution (for ≥ 2 consecutive weeks in the year prior

---

to the informed consent procedure) and specific signs or symptoms occurring during the screening period ([Appendix 4](#)) confirmed before dialysis on the start day of treatment.

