### 8.6.2 Rationale for the sample size

#### 8.6.2.1 Double-blind period

In a Japanese phase II clinical study (MR13A9-4), the change from baseline in the mean NRS score at Week 4 of the treatment period (mean  $\pm$  standard deviation) was  $-2.15 \pm 1.98$  in the placebo group and  $-3.22 \pm 2.09$  in the MR13A9 0.5 µg/kg group. The difference for the MR13A9 0.5 µg/kg group versus the placebo group at Week 4 of the treatment period was  $-1.04 \pm 0.35$  (adjusted mean  $\pm$  standard error).

For the primary variable of change from baseline in the mean NRS score at Week 4 of the double-blind period, its mean difference for the MR13A9 0.5 µg/kg group versus the placebo group was assumed to be  $-1.0$ , with a common standard deviation of  $2.0$ . Assuming a two-sided significance level of  $5\%$  and a statistical power of  $90\%$ , the sample size required to confirm the superiority of the MR13A9 0.5 µg/kg group to the placebo group using a two-sample t-test was calculated to be 86 subjects per group.

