12.1.5 Occurrence of adverse events and adverse drug reactions (by time of onset)

The events to be tabulated are shown in [Table 12.1.5-1](#).

The time to onset of adverse events will be classified into the time categories as shown in [Table 12.1.5-2](#), and the number of subjects experiencing events and the incidences of events by primary SOC and PT will be presented for each category for all events, events leading to death, serious events other than death, events leading to interruption, and events leading to discontinuation. The number of subjects experiencing events and the incidence of events

throughout the entire period, regardless of the time of onset, will also be presented. Discontinued subjects will be included in the denominator when calculating incidence for the time categories included in the tabulation periods shown in [Table 12.1.5-1](#), but will be excluded from the denominator for the later time categories.

Table 12.1.5-1 Events to be tabulated

Period	Tabulation time periods	Events to be tabulated
Entire study period	From the start of study treatment to the end of the follow-up period	
 Events occurring between the start of study treatment and the end of the follow-up period Adverse events of special interest occurring between the start of study treatment and the end of the follow-up period
	From the start of study treatment to the end of the extension period	
 Events occurring between the start of study treatment and the end of the extension period Adverse events of special interest occurring between the start of study treatment and the end of the extension period

Table 12.1.5-2 Time category

Time category (unit: weeks)	Time to onset of adverse event (unit: days)
< 6	< 43
< 12	< 85
12 ≤ < 24	85 ≤ < 169
24 ≤ < 36	169 ≤ < 253
36 ≤ < 48	253 ≤ < 337
48 ≤	337 ≤

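### The entire-study adverse event incidence is a crude proportion over all extension entrants, so with early exits and continuing events it can understate the risk to Week 58

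*Protocol*

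**What the plan says.** Protocol 14.6.1 item 1 sets the headline adverse event output: "The number of events, the number of subjects experiencing events, the incidence of events and its two-sided 95% confidence interval will be presented". Items 2 and 3 give numbers and incidences without an interval. SAP 12.1.1 to 12.1.3 follow the same pattern. For the entire study period, events count from the first dose in the double-blind period to the end of follow-up; SAP 12.1 adds a version that stops at the end of the extension.

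Neither document writes out the denominator. Protocol Table 14.2.2-1 and SAP Table 3-2 define the entire-study safety groups (MR-MR and P-MR) as treated subjects who entered the extension. The implied denominator is therefore every entrant in the group. The adverse event sections plan no person-time rate, Kaplan-Meier estimate or cumulative incidence.

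SAP 12.1.5 handles leavers differently in the table by time of onset: "Discontinued subjects will be included in the denominator when calculating incidence for the time categories included in the tabulation periods" shown in its Table 12.1.5-1, and they drop out of the denominators of later categories. The same section also presents a whole-period incidence regardless of onset time, with no such adjustment.

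On extension size, the synopsis says: "The study will enroll 100 subjects who complete 58-week treatment". Protocol 8.6.2.2 takes that number from a guideline on long-term exposure.

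**The concern.** Protocol 8.2.5 gives long-term safety as the reason for the 52-week extension. In a crude proportion, a subject who leaves event-free at Week 10 carries the same weight as one observed event-free to Week 58. Early exit is foreseen: Protocol 5.3.1 lists subject request, lack of efficacy and seven consecutive missed extension doses, among other reasons. Adverse events are collected whatever their cause, so they can go on accruing through the year.

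Two things are at stake. First, a reader who takes the incidence as the risk over 58 weeks may take it too low. Second, the same measure is used for the 6-week double-blind period, for the Week 34 tabulations that support the approval application (SAP 6.3.2) and for the full period. These figures rest on different observation times and have no common time base. The same holds for MR-MR against P-MR if drop-out differs between them.

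**Working it through.** **The plan's own figure.** The only calculated sample size is for the double-blind period: "two-sample t-test was calculated to be 86 subjects per group". With a difference of 1.0, SD 2.0, two-sided 5% and 90% power, the normal approximation gives 85 per group. The t-test solves at 85.03, so 86, with power 90.3%. The figure reproduces. It concerns the Week 4 comparison only. The 100 completers have no formula behind them.

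**Assumed inputs** (the documents give none for the extension): 160 entrants; C completers, with C = 100, 120 or 140; exits spread evenly over Weeks 6 to 58 and unrelated to event risk; a true 58-week risk of 10%. The extra follow-up week is ignored.

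**Constant event rate.**
- Weekly hazard λ = −ln(0.90)/58 = 0.001817.
- Mean risk while observed, for a leaver: 1 − [exp(−6λ) − exp(−58λ)]/(52λ) = 1 − (0.9892 − 0.9000)/0.0945 = 5.61%.
- Reported proportion = [C × 10% + (160 − C) × 5.61%]/160.

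| Completers | Mean weeks observed | Reported for a true 10% | Relative shortfall |
|---|---|---|---|
| 100 | (100×58 + 60×32)/160 = 48.25 | 8.35% | 16.5% |
| 120 | (120×58 + 40×32)/160 = 51.5 | 8.90% | 11.0% |
| 140 | (140×58 + 20×32)/160 = 54.75 | 9.45% | 5.5% |

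**Event timing** (160 entrants, 100 completers, true 10%).
- Half the events before Week 6, then a constant rate: leaver risk 1 − (0.95 − 0.90)/ln(0.95/0.90) = 7.52%; reported (10 + 60 × 0.0752)/160 = 9.1%.
- 80% before Week 6: leaver risk 1 − (0.92 − 0.90)/ln(0.92/0.90) = 9.00%; reported 9.6%.
- All before Week 6: 10%, no shortfall.
- All in Weeks 34 to 58: leaver risk (24/52) × [1 − 0.10/(−ln 0.90)] = 2.35%; reported (10 + 60 × 0.0235)/160 = 7.1%.

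**A second drop-out model.** With a constant drop-out hazard over the 52 extension weeks and a constant event rate, a true 10% is reported as 9.2% (120 entrants, 100 completers), 8.7% (140, 100) and 8.0% (172, 100, the bounding case in which everyone enrolled enters). The two models agree in direction and order of size.

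**Confidence interval.** The documents name no method, so the exact binomial interval is used. At about 80 per group, 7/80 (8.8%) gives 3.6% to 17.2%. Pooled, 13/160 (8.1%) gives 4.4% to 13.5%. Both cover 10%. The interval sits lower but still contains the true value at these sizes.

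**What SAP 12.1.5 recovers.** In the bounding 172/100 case, chaining the non-overlapping onset intervals, using first events only, gives 9.5%, 28.7% and 48.2% for true risks of 10%, 30% and 50%. The unadjusted proportions are 8.0%, 24.3% and 41.1%.

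**The case against.** The strongest reply is that the plan already deals with most of this. SAP 12.1.5 reduces the later denominators by SOC and PT, for all events, deaths, other serious events, interruptions and discontinuations, and for events of special interest. Discontinuations with reasons, dose counts and treatment duration are also tabulated, so unequal exposure is visible. This stands in part. However, the table has no stated interval, no cumulative estimate and no first-event rule, and its first two categories overlap. The chaining above would be the reader's own calculation.

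Second, Protocol 8.2.5 reports that all adverse drug reactions in the phase II study MR13A9-4 came before Week 6. Entrants have by definition not been withdrawn before then, so reactions that early would be fully captured. This is a fair limit on the size. But that study lasted 8 weeks and cannot show what happens later, which is what the extension is for.

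Third, neither document calls the figure a 58-week risk, and the Fisher tests are confined to the double-blind period. As the proportion of subjects with an event while observed, it is valid and worth keeping. Subjects who leave because of an adverse event are already in the numerator, which limits the shortfall.

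A reader might also infer that 100 completers against 172 enrolled means the plan expects about 42% to leave. It does not say so. The 100 is an exposure target, the 172 is double-blind enrolment, and subjects who never enter the extension are outside these groups.

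**Conclusion.** The point holds in conditional form. The whole-period incidence and its interval are crude proportions over extension entrants. They can understate the risk to Week 58 if subjects leave event-free and events continue after Week 6, and they do not compare like with like across different observation times. Under the 160-entrant, constant-rate assumptions, a true 10% is reported as about 8.4% to 9.5%. Early clustering shrinks the gap to nothing; late events widen it.

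Two stronger readings are not supported. One is that the long-term risk will be understated: that depends on retention and event timing, which the documents do not give. The other is that the confidence interval is invalid or too narrow: it can shift down, but it still covers a true 10% at the sizes considered. The efficacy conclusions are unaffected. This is an inexpensive improvement to the safety reporting.

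**What to change.** In SAP 12.1.1 to 12.1.3, for the entire study period:

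- State the denominator and keep the crude columns as planned.
- Add subjects with a first event per 100 patient-years (time from first dose to first event or end of observation) and total events per 100 patient-years, each with a 95% confidence interval.
- Add a Week 58 cumulative incidence with a 95% confidence interval for any adverse drug reaction and for adverse events of special interest. Use Kaplan-Meier, or a competing-risk estimate that accounts for death. Note that either treats other early exits as unrelated to event risk.
- Present the rates beside the SAP 12.1.5 onset table, because a single rate over a long exposure dilutes events that cluster early.

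The cost is SAP wording and a little programming. Dates of onset, dosing and discontinuation are already collected, so study conduct does not change. The long-term figures may look slightly less favourable.
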